## Criteria for Evaluation

The primary endpoint of this study is an individual subject achieving Palmoplantar Physician Global Assessment (ppPGA) of 0 (clear) or 1 (almost clear/minimal) after 24 weeks of treatment. The ppPGA is based on the Investigators Global Assessment (IGA) modified version 11, specifically applied to the hands and/or feet: 0 (clear), 1 (almost clear/minimal), 2 (mild), 3 (moderate), 4 (marked/moderate-to-severe), 5 (severe).

The secondary endpoints of this study include the following:

- Percentage of patients achieving ppPGA of 0 or 1 at weeks 8, 12 and 16
- Photography (hands and/or feet only) to assess treatment response at weeks 0, 2, 8, 12, 16 and 24
- Patient-reported outcomes evaluated by Dermatology Quality of Life Index (DLQI) to be determined at weeks 2, 8, 12, 16 and 24
- Treatment satisfaction evaluated by a Numerical Rating Scale (NRS) to be determined at weeks 2, 8, 12, 16 and 24

The DLQI is a 10 question dermatology-specific quality of life questionnaire covering the following topics: symptoms, embarrassment, shopping and home care, clothes, social and leisure, sport, work or study, close relationships, sex, treatment. Each question refers

to the impact of the skin disease on the patient's life over the previous week.

The NRS for treatment satisfaction consists of 1 question: "Consider all the good and bad things about this treatment. Overall, how satisfied are you with the treatment?" Answer options: -3 (very dissatisfied), -2 (moderately satisfied), -1 (mildly satisfied), 1 (mildly satisfied), 2 (moderately satisfied), 3 (very satisfied).

There are no anticipated primary or secondary safety endpoints that would cause a study subject's participation to end due to safety.

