## Brief Summary of Research

The purpose of this research study is to examine the effect of Duobrii® (halobetasol propionate 0.01%/tazarotene 0.045% lotion, HP/TAZ) on plaque type psoriasis of the hands and/or feet. It is an investigator-initiated, single-arm, open-label study that will include 22 subjects. A thin layer of HP/TAZ will be applied to affected areas of palms and/or soles once a day. Treatment response will be clinically evaluated using the Palmoplantar Physician Global Assessment (ppPGA), which is a 5-point scale specifically applied to the hands and/or feet: 0 (clear), 1 (almost clear/minimal), 2 (mild), 3 (moderate), 4 (marked/moderate-to-severe), 5 (severe). The primary objective of the study is to evaluate the percentage of subjects achieving ppPGA of 0 or 1 after 24 weeks of treatment. Secondary objectives include evaluation of treatment response at earlier timepoints (Weeks 2, 8, 12, 16 and 24), including serial photography (also taken at week 0), patient-reported outcomes, and treatment satisfaction evaluation throughout the study period. In addition, safety and tolerability will be assessed by physical exam findings, adverse event monitoring, and concomitant medication review. Previous therapies used and failed will be captured for each subject.

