These phase 3 studies did not include a sub-analysis of the effect of HP/TAZ on psoriasis of the hands and/or feet. Given that topical steroids and topical retinoids are separately recommended as treatment options for psoriasis of the hands and/or feet, an agent that safely combines these medications – and that has demonstrated safety and efficacy in generalized psoriasis – offers a potential treatment for psoriasis of the hands and/or feet.

The purpose of the study described in this protocol is to evaluate the effect of HP/TAZ on plaque type psoriasis of the hands and/or feet after 24 weeks of daily treatment. In addition, given the impact of this variant of psoriasis on QoL and the relative lack of currently available treatment options, this study will also evaluate the impact of HP/TAZ treatment on patient-reported QoL measures and treatment satisfaction scoring.

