### Study Timeline:

- An individual subject will participate in study activities for a total of 24 weeks from initial screening/baseline visit at Week 0 to the final study visit at Week 24.
- It is anticipated that it will take up to 12 months to enroll all study subjects.

- It is estimated that this study will be completed, including completion of primary analyses, by the end of 2022.

Potential subjects will be screened for eligibility based on the inclusion and exclusion criteria indicated below.

*Inclusion Criteria*

1. Subject is able to provide written, informed consent and comply with the study protocol.
2. Subject is at least 18 years of age.
3. Subject has a diagnosis of plaque-type palmar and/or plantar psoriasis.
4. Patient has at least one psoriatic plaque outside of the palms and soles or psoriatic nail findings.
5. Subject has a ppPGA  $\geq 3$  at screening/baseline visit.
6. Subject is using adequate birth control during the study period as defined as follows:
  - a. Option 1: Any one of the following highly effective methods: hormonal contraception (oral, injection, implant, transdermal patch, vaginal ring); intrauterine device (IUD); tubal ligation; or partner's vasectomy;

OR

- b. Option 2: Male or female condom (latex condom or nonlatex condom NOT made out of natural [animal] membrane [for example, polyurethane]; PLUS one additional barrier method: (a) diaphragm with spermicide; (b) cervical cap with spermicide; or (c) contraceptive sponge with spermicide.

OR

- c. Option 3: Abstinence from sex when it is a lifestyle choice, and not just a social circumstance.

*Exclusion Criteria*

1. Subject is not able to provide written, informed consent and comply with the study protocol.
2. Subject is less than 18 years of age.
3. Subject has non-plaque type psoriasis on the hands and/or feet.
4. Patient does not have any evidence of psoriasis elsewhere.

5. Subject has concurrent cutaneous disease affecting the hands and/or feet that would interfere with assessments.
6. Subject has a ppPGA < 3 at screening/baseline visit.
7. Subject refuses to discontinue concomitant prescription medications on hands and/or feet.
8. Subject has used topical prescription treatments or received phototherapy treatment for psoriasis within 2 weeks of screening/baseline visit.
9. Subject has used intralesional kenalog within 4 weeks of screening/baseline visit.
10. Subject has taken oral treatments for psoriasis within 4 weeks of screening/baseline visit.

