## **Study Procedures & Guidelines**

The study is designed to include six study visits over 24 weeks. The procedures performed at each study visit are detailed below. All procedures will be performed at the single study site. They will also be instructed to store the investigational drug at 20 to 25 °C (68 to 77 °F), and to not freeze the drug.

A table detailing the study procedures is found in Appendix 1. All study visits and procedures will be documented in source documents created specifically for this study that will be completed in accordance with Good Clinical Practice (GP) documentation principles (i.e. attributable, legible, contemporaneous, original, accurate, enduring, available and accessible, complete, consistent, credible, and corroborated).

- I. Week 0 (Screening/Baseline)
  - A. Review Inclusion/Exclusion criteria
  - B. Obtain written informed consent
  - C. Review medical history and previous failed therapies

- D. Review concomitant medications
- E. Perform physical examination
- F. Obtain urine pregnancy test (for pre-menopausal female subjects only)
- G. Evaluate ppPGA
- H. Obtain photographs of affected areas
- I. Dispense study drug

II. Week 2

- A. Review adverse events
- B. Review concomitant medications
- C. Evaluate ppPGA
- D. Administer DQLI
- E. Administer NRS for treatment satisfaction
- F. Obtain photographs of affected areas
- G. Dispense study drug
- H. Collect study drug

III. Week 8

- A. Review adverse events
- B. Review concomitant medications
- C. Evaluate ppPGA
- D. Administer DQLI
- E. Administer NRS for treatment satisfaction
- F. Obtain photographs of affected areas
- G. Dispense study drug
- H. Collect study drug

IV. Week 12

- A. Review adverse events
- B. Review concomitant medications
- C. Evaluate ppPGA
- D. Administer DQLI
- E. Administer NRS for treatment satisfaction
- F. Obtain photographs of affected areas

V. Week 16

- A. Review adverse events
- B. Review concomitant medications
- C. Evaluate ppPGA
- D. Administer DQLI

- E. Administer NRS for treatment satisfaction
- F. Obtain photographs of affected areas
- G. Dispense study drug
- H. Collect study drug

VI. Week 24

- A. Review adverse events
- B. Review concomitant medications
- C. Evaluate ppPGA
- D. Administer DQLI
- E. Administer NRS for treatment satisfaction
- F. Obtain photographs of affected areas
- G. Collect study drug

VII. Early Termination

- A. Review adverse events
- B. Review concomitant medications

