## Protocol Violations

Subjects may withdraw from the trial at any time at their request (verbal or written), or they may be withdrawn at any time at the discretion of the Sponsor, PI, or designee for safety, behavioral, or administrative reasons. Subjects may be withdrawn from this study without their consent if the research study is being stopped; or if the instructions of the study team have not been followed.

Any enrolled subject who will not be completing the duration of the study will be asked to complete an Early Termination study visit, consisting of the procedures indicated below. In addition, the reason for Early Termination will be recorded in the source documents.

- 1) Review medical history
- 2) Review concomitant medications
- 3) Perform physical examination
- 4) Obtain urine pregnancy test (for pre-menopausal female subjects only)
- 5) Evaluate ppPGA
- 6) Administer DQLI

- 7) Administer NRS for treatment satisfaction
- 8) Obtain photographs of affected areas

If a subject is unable or unwilling to complete an Early Termination visit, this will be documented in the source documents.

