8.	Over the last week, how much has your skin created problems with your partner or any of your close friends or relatives ?	Very much A lot A little Not at all	   	Not relevant 
9.	Over the last week, how much has your skin caused any sexual difficulties ?	Very much A lot A little Not at all	   	Not relevant 
10.	Over the last week, how much of a problem has the treatment for your skin been, for example by making your home messy, or by taking up time?	Very much A lot A little Not at all	   	Not relevant 

Please check you have answered **EVERY** question. Thank you.

Source: Finlay AY, Khan GK. Dermatology Life Quality Index (DLQI)--a simple practical measure for routine clinical use. *Clin Exp Dermatol*. 1994;19(3):210-216.

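### No DLQI is taken before treatment, so this single-arm trial cannot show how far quality of life moved from its pre-treatment level

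*Combined protocol and SAP*

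**What the plan says.** All statements of DLQI timing in the plan agree.

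- **Criteria for Evaluation**, secondary endpoints: "Patient-reported outcomes evaluated by Dermatology Quality of Life Index (DLQI) 2 to be determined at weeks 2, 8, 12, 16 and 24". The synopsis lists the same five visits. In both lists, photography does include Week 0.
- **Brief Summary of Research**: response is assessed at "earlier timepoints (Weeks 2, 8, 12, 16 and 24), including serial photography (also taken at week 0), patient-reported outcomes, and treatment satisfaction evaluation". Only photography is singled out as also taken at Week 0.
- **Study Procedures & Guidelines**: the Week 0 list (items A to I) has ppPGA and photographs but no DLQI. It closes with "I. Dispense study drug".
- **Appendix 1**: the Week 0 cell of the DLQI row is empty, while ppPGA and photography are marked.
- **Early Termination** (Study Procedures & Guidelines, and Protocol Violations): a DLQI is included, but only after treatment has started.

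The aim is in the **Background**: "this study will also evaluate the impact of HP/TAZ treatment on patient-reported QoL measures and treatment satisfaction scoring". Study Design confirms one open-label arm without randomization. Statistical Methods & Considerations gives no analysis for the DLQI.

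**The concern.** An effect of treatment on quality of life needs a comparison, either with untreated patients or with the same patients before treatment. This trial has no control arm and plans no DLQI before the first application, so the five later scores have nothing pre-treatment to be set against.

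The primary endpoint escapes this problem because every patient must enter with ppPGA of 3 or more, so a 0 or 1 at Week 24 implies improvement. No eligibility criterion concerns the DLQI. A low score at Week 24 could mean a large gain or a patient who scored low at entry, and the data as planned cannot tell these apart.

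The trial could therefore report how patients score on treatment, but not how far they moved, which is the natural reading of the aim in the Background. The loss is permanent for each patient once treatment begins.

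**Working it through.** The plan gives no numerical target for the DLQI, so there is no figure to reproduce. The sample size of 22 is justified on ppPGA alone.

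**1. Pre-treatment scores available.** From the schedule: 0 of 22 patients, hence 0 pairs for change from the untreated state.

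**2. Can Week 2 serve as baseline?**
- Each DLQI question refers "to the impact of the skin disease on the patient's life over the previous week", so the Week 2 form covers roughly days 8 to 14 of daily application.
- Item 10 asks about the burden of treatment "for your skin been, for example by making your home messy, or by taking up time". At Week 2 that can already include the study lotion.
- The first score comes after 14 of 168 treatment days (14/168 = 8.3%). This is a share of time, not a share of effect.

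Let *f* be the share of the total Week 0 to Week 24 change reached by Week 2. Change from Week 2 then shows 1 − *f* of the total. The documents give no value for *f*; these are assumed.

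| Assumed *f* | Share of total change seen from Week 2 |
|---|---|
| −0.25 (early worsening) | 125% |
| 0 | 100% |
| 0.25 | 75% |
| 0.50 | 50% |

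The error can go either way. Adverse Effects and Reporting lists contact dermatitis and application site pain among the common reactions, so early worsening is conceivable.

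**3. Early leavers.** Under Protocol Violations, "Any enrolled subject who will not be completing the duration of the study will be asked to complete an Early Termination study visit". A patient who leaves before Week 2 would have that one DLQI at most, and so no change score of any kind. Change from Week 2 is thus computed only in those who stayed.

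**4. What a Week 0 form would provide.** The 95% CI half-width for mean paired change is t(0.975, n−1)/√n × SD of change.
- n = 22: 2.080/4.690 = 0.443 SD
- n = 18 (assumed loss of 4): 2.110/4.243 = 0.497 SD

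The documents give no SD of DLQI change. Over an assumed 5 to 8 points:

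| Pairs | SD 5 | SD 8 |
|---|---|---|
| 22 | ±2.2 | ±3.5 |
| 18 | ±2.5 | ±4.0 |

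With 22 pairs, a two-sided 5% paired t-test has 80% power for a mean change of 0.63 SD.

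**5. Cost in forms.** 5 × 22 = 110 as planned; 6 × 22 = 132 with Week 0.

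**The case against.** The strongest reply is that no stated endpoint fails. The secondary endpoint is only the DLQI at five visits. Change from baseline is never named, Study Objectives does not mention quality of life, and the omission is consistent throughout. The Background sentence also applies the word impact to treatment satisfaction, which has no pre-treatment value, so it need not mean change from Week 0.

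Much of this is true. The listed endpoint can be met descriptively through on-treatment levels, the proportion below a chosen level, and change from Week 2. But consistency does not make the scores interpretable, and no reason for the omission is given. Satisfaction with the study drug cannot exist before the drug is used; the effect of the disease on daily life can.

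It is also fair to say that the values of *f* and the SD range are assumptions and do not measure the harm. The measure of the defect is 0 of 22. The confidence intervals show only what the remedy would deliver.

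Three limits of the remedy stand:
- A before-after change without controls cannot be attributed to treatment.
- Item 10 may not be relevant at Week 0 yet be relevant later, so the total score is not perfectly symmetric.
- Adding a baseline does not by itself settle how Early Termination scores are used.

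These call for care in the analysis. They are not reasons to leave the baseline out.

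**Conclusion.** The concern holds and should be fixed. As scheduled, 0 of 22 patients will have a pre-treatment DLQI, so the study cannot estimate change in quality of life from the untreated state. Change from Week 2 omits whatever happened in the first two weeks, by an unknown amount in either direction, and leaves out the earliest leavers. The count of 0 follows directly from the schedule and rests on no assumption. The early-effect shares, the SD of change and the loss of four patients are assumptions, because the documents state none of them. The primary ppPGA endpoint and the descriptive reporting of on-treatment DLQI are not affected.

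**What to change.** 1. Add the DLQI to the Week 0 list in Study Procedures & Guidelines, after consent and before study drug is dispensed. Mark the Week 0 cell in Appendix 1, and add Week 0 to the DLQI bullets in the synopsis and Criteria for Evaluation.
2. Define the endpoint as mean paired change from Week 0 with a 95% CI at each later visit, reported beside on-treatment levels. State how Early Termination scores and missed visits are handled, and show the change without item 10 as a check.
3. State that this change is uncontrolled. Patients are selected for ppPGA of 3 or more, so regression to the mean may contribute. Exclusion criterion 8 ("Subject has used topical prescription treatments or received phototherapy treatment for psoriasis within 2 weeks of screening/baseline visit") places the Week 0 recall week inside a period without those therapies, so recovery after their withdrawal may also contribute.
4. Leave the satisfaction NRS starting at Week 2. As a clerical correction only, align its labels for −2 and −1 in Criteria for Evaluation and Appendix 1 with the form in Figure 2.

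The cost is one 10-question form per patient at an existing visit, 22 more forms in all, and a brief amendment, with no extra visit or staff. The full 22 pairs are possible only if the change is made before the first patient is treated; the documents do not give recruitment status.

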## Subject Selection

Potential subjects will be recruited from routine clinical appointments at Mount Sinai dermatology clinics as well as Mount Sinai-affiliated dermatologists and other referring dermatologists.

## Concomitant Therapies

All concomitant therapies must be recorded throughout the study period, from Screening/Baseline through Week 24. Subjects will be asked about concomitant therapies as part of the review of medical history at every study visit. With respect to specific classes of concomitant therapies:

- **Topical therapies:** Topical therapies that could affect the ppPGA evaluations (eg, corticosteroids, tar, anthralin, calcipotriene, tazarotene, methoxsalen, pimecrolimus, tacrolimus) are not permitted. The only allowable concomitant treatments throughout the study are non-medicated topical moisturizers. However, subjects should not use non-medicated topical moisturizers on the day of a study visit.
- **Phototherapy:** The use of phototherapy is not permitted at any time during the study.
- **Systemic therapy:** The use of systemic psoriasis medications is not permitted at any time during the study. These medications include those targeted for reducing TNF (including but not limited to infliximab or etanercept), drugs targeted for reducing IL-12, IL-17, or IL-23 (including but not limited to ustekinumab, tildrakizumab, secukinumab, ixekizumab, or brodalumab), alpha-4 integrin antagonists (including but not limited to natalizumab), systemic steroids, any conventional systemic therapy that could affect ppPGA evaluation (including but

not limited to methotrexate, cyclosporine, acitretin), and any other biological agent or other systemic medication that could affect the ppPGA evaluation.

- Other therapies: Every effort should be made to keep subjects on stable frequency and dosing of concomitant medications for general medical conditions. Such medications should be recorded at Week 0 (Screening/Baseline Visit) and if any changes to frequency or dosing are made during the duration of the study, such changes should be reported by the patient and recorded in the source documents.

## **Study Treatments**

Upon enrollment in the study, each subject will be given a supply of HP/TAZ at visits 0,2,8,16 to be used over the 24 weeks. Each subject will be instructed to apply a thin layer HP/TAZ to affected areas of palms and/or soles once a day for the duration of the study (i.e. daily treatment for 24 weeks).

All study treatments will be completed by the subject and will occur in the home setting. Subjects will be encouraged to record and report any missed treatments. Patients will be allowed to use OTC moisturizers, but should not apply them the days of their visits.

## **Study Procedures & Guidelines**

The study is designed to include six study visits over 24 weeks. The procedures performed at each study visit are detailed below. All procedures will be performed at the single study site. They will also be instructed to store the investigational drug at 20 to 25 °C (68 to 77 °F), and to not freeze the drug.

A table detailing the study procedures is found in Appendix 1. All study visits and procedures will be documented in source documents created specifically for this study that will be completed in accordance with Good Clinical Practice (GP) documentation principles (i.e. attributable, legible, contemporaneous, original, accurate, enduring, available and accessible, complete, consistent, credible, and corroborated).

- I. Week 0 (Screening/Baseline)
  - A. Review Inclusion/Exclusion criteria
  - B. Obtain written informed consent
  - C. Review medical history and previous failed therapies

- D. Review concomitant medications
- E. Perform physical examination
- F. Obtain urine pregnancy test (for pre-menopausal female subjects only)
- G. Evaluate ppPGA
- H. Obtain photographs of affected areas
- I. Dispense study drug

II. Week 2

- A. Review adverse events
- B. Review concomitant medications
- C. Evaluate ppPGA
- D. Administer DQLI
- E. Administer NRS for treatment satisfaction
- F. Obtain photographs of affected areas
- G. Dispense study drug
- H. Collect study drug

III. Week 8

- A. Review adverse events
- B. Review concomitant medications
- C. Evaluate ppPGA
- D. Administer DQLI
- E. Administer NRS for treatment satisfaction
- F. Obtain photographs of affected areas
- G. Dispense study drug
- H. Collect study drug

IV. Week 12

- A. Review adverse events
- B. Review concomitant medications
- C. Evaluate ppPGA
- D. Administer DQLI
- E. Administer NRS for treatment satisfaction
- F. Obtain photographs of affected areas

V. Week 16

- A. Review adverse events
- B. Review concomitant medications
- C. Evaluate ppPGA
- D. Administer DQLI

- E. Administer NRS for treatment satisfaction
- F. Obtain photographs of affected areas
- G. Dispense study drug
- H. Collect study drug

VI. Week 24

- A. Review adverse events
- B. Review concomitant medications
- C. Evaluate ppPGA
- D. Administer DQLI
- E. Administer NRS for treatment satisfaction
- F. Obtain photographs of affected areas
- G. Collect study drug

VII. Early Termination

- A. Review adverse events
- B. Review concomitant medications
- C. Evaluate ppPGA
- D. Administer DQLI
- E. Administer NRS for treatment satisfaction
- F. Obtain photographs of affected areas
- G. Collect study drug
- H. Physical examination

